Protocol Synopsis CP13-001
The WEB[®] Intrasaccular Therapy Study
(WEB-IT)

Study Sponsor

Sequent Medical, Inc.

[name], [name]

USA

DISCLOSURE STATEMENT

This document contains information that is confidential and proprietary to Sequent Medical, Inc. (Sequent). This information is being provided to you solely for the purpose of evaluating or conducting a clinical study for Sequent. You may disclose the contents of this document only to study personnel under your supervision who need to know the contents for this purpose and to your Institutional Review Board (IRB) or Ethics Committee (EC) otherwise; the contents of this document may not be disclosed without the prior authorization from Sequent. The foregoing shall not apply to disclosure required by governmental regulations or laws. Any supplemental information that may be added to this document also is confidential and proprietary to Sequent and must be kept in confidence in the same manner as the contents of this document.

The WEB[®] Intracascular Therapy Study (WEB-IT)

1 Study Summary

Protocol:	CP13-001 Rev.3.1
Study Name:	The WEB [®] Intracascular Therapy Study (WEB-IT)
Study Purpose:	To demonstrate the safety and effectiveness of the WEB Aneurysm Embolization System for the treatment of intracranial wide-neck bifurcation aneurysms
Study Device:	The WEB Aneurysm Embolization System
Study Design:	Prospective, single-arm, multicenter, international interventional cohort
Sample Size	Up to 150 treated subjects
Study Population:	Adults (18-75 years of age) with intracranial wide-neck aneurysms located at arterial bifurcations (see eligibility criteria)
Study Duration:	Each subject will participate for at least 5 years. Total study duration will be approximately 6 years.
Primary Endpoints:	
The study's primary effectiveness endpoint is the proportion of subjects with complete aneurysm occlusion without retreatment, recurrent subarachnoid hemorrhage, without significant parent artery stenosis (>50% stenosis) at one year after treatment. A subject will be considered an effectiveness success upon meeting all of the above criteria.
 
The study's primary safety endpoint is the proportion of subjects with death of any nonaccidental cause or any major stroke (defined as an ischemic or hemorrhagic stroke resulting in an increase of 4 points or more on the National Institutes of Health Stroke Scale) within the first 30 days after treatment or major ipsilateral stroke or death due to neurologic cause from day 31 to the 1 year after treatment. A subject will be considered a safety failure upon meeting any of the above criteria. All safety events will be adjudicated by an independent clinical events adjudicator.
 
The study will be interpreted as a success if both of the primary effectiveness and primary safety endpoints are met.

CLINICAL PROTOCOL SYNOPSIS

Secondary Endpoint:	The study's secondary endpoint is the proportion of subjects with angiographic aneurysmal recurrence defined as aneurysm growth or recanalization at one year after treatment.
Other Endpoints:	
Secondary analyses include:
 
 • Technical success • IA occlusion status at other time points (6 mo, 2, 5 yrs) • Change in mRS (for unruptured subjects only) • % Aneurysm occlusion • Proportion of IAs with each occlusion category at all angiographic follow-up time points. • Durability of occlusion – defined as “Same”, “Better”, “Worse” when comparing the 1 year angiographic result with the 6 month angiographic result
Inclusion Criteria	
 1. Patient must be 18-75 years of age at the time of screening. 2. Patient must have a single ruptured or unruptured IA requiring treatment. If the subject has an additional IA requiring treatment, the additional IA must not require treatment within 60 days of the index procedure. 
Definition: For the purposes of this study a ruptured IA patient is defined as a patient with computed tomography (CT), magnetic resonance imaging (MRI), or lumbar puncture (LP) evidence of subarachnoid hemorrhage attributed to the index aneurysm within the last 60 days.
 
 3. The index IA to be treated must have the following characteristics: 
 a. Saccular in shape b. Located in basilar apex (BA), middle cerebral artery (MCA) bifurcation, internal carotid artery terminus (ICAt), anterior communicating artery complex (ACom) c. Dome-to-Neck (DN) ratio ≥ 1 d. Diameter of the IA is appropriate for treatment with the WEB Aneurysm Embolization System per device Instructions for Use e. Wide-neck IA with neck size $\geq 4\text{mm}$ or Dome-to-Neck (DN) < 2; 4. Patient has an IA that is appropriate for treatment with WEB without the use of additional implanted devices; 5. If the IA previously ruptured, patient must be neurologically stable with Hunt & Hess Score of I or II. 6. Patient must be able to comply with all aspects of the screening, evaluation, treatment, and the postprocedure follow-up schedule. Patient must sign and date an IRB/EC-approved written informed consent prior to initiation of any study procedures. 7. Patient must sign and date an IRB/EC-approved written informed consent prior to initiation of any study procedures.

[figure not shown]
CLINICAL PROTOCOL SYNOPSIS

Exclusion Criteria	
 1. Patient has an IA with characteristics unsuitable for endovascular treatment; 2. Microcatheter could not reach patient's index aneurysm to allow necessary access to treat with study device. 3. Patient has vessel characteristics, tortuosity or morphology which could preclude safe access and support during treatment with study device; 4. Patient has vascular disease or other vascular anomaly so as to preclude the necessary access to the aneurysm for use of the study device. 5. Patient has clinical, angiographic or CT evidence of vasospasm, vasculitis, or intracranial tumor (except small meningioma) or any other intracranial vascular malformations on presentation; 6. Patient has conditions placing them at high risk for ischemic stroke or has exhibited ischemic symptoms such as transient ischemic attacks, minor strokes, or stroke-in-evolution within the prior 60 days; 7. Patient has any circulatory, neurovascular, cardiovascular, or neurologic conditions that have resulted in unstable neurological symptoms 8. Patient has mRS \geq 2 prior to presentation or rupture (as applicable); 9. Patient has had an SAH from a nonindex IA or any other intracranial hemorrhage within 90 days; 10. Patient has physical, neurologic or psychiatric conditions which preclude his/her ability to comply with all aspects of the screening, evaluation, treatment, and the postprocedure follow-up schedule; 11. Patient's index IA was previously treated; 12. Patient is taking anticoagulants or has a known blood dyscrasia, coagulopathy, or hemoglobinopathy; 13. Patient is pregnant; 14. Patient has known hypersensitivity, which cannot be medically treated, to any component of the study device, procedural materials, or medications commonly used during the procedure; 15. Patient is concurrently involved in another investigational study or a postmarket study that could affect the safety and effectiveness of IA treatment with the study device or with the study's follow-up schedule; 16. Patient has an acute life-threatening illness other than the neurological disease to be treated in this trial; 17. Patient has a life expectancy of less than 5 years due to other illness or condition (in addition to an intracranial aneurysm).
Study Procedures:	Subjects will be screened for study eligibility after giving informed consent. The WEB embolization procedure will be performed in the digital angiographic suite using standard angiographic techniques.
Schedule of Examinations:	Screening (Day -30 to Day 0) Procedure

CLINICAL PROTOCOL SYNOPSIS

	Discharge 30-day follow-up (mRS per office or telephone update) Six month follow-up (office visit and angiographic follow-up) One year follow-up (office visit and angiographic follow-up) Two year and four year follow-up (office visit per standard of care or telephone update) Three year and five year follow-up (office visit and imaging follow-up per standard of care)
--	---

Figure 1. Diagram of Study Flow.

CLINICAL PROTOCOL SYNOPSIS

Table 1. Schedule of Assessments.

Parameter	Screening	Procedure	Discharge	30-Day Follow-Up	6-Month Follow-Up	1-Year Follow-Up	2- and 4-Year Follow-Up	3- and 5-year Follow-Up
Health history	X							
Physical examination	X	X	X		X	X		X
Neurological examination	X				X	X		X
Site and subject information	X							
Aneurysm information (size, location, etc.)	X	X						
Rupture status	X							
Hunt and Hess Grade (ruptured aneurysms only)	X							
Microcatheter(s) used		X						
Ancillary devices used (eg, stent, balloon used)		X						
Medications used	X	X	X		X	X		X
Size and lot number of WEB device(s) used		X						
WEB procedure fluoroscopy time		X						
Total procedure fluoroscopy time		X						
3D angiographic imaging	X	X			X	X	Optional	X*
Additional imaging per standard of care							X	X
Occlusion assessments (Core Lab)			X		X	X	Optional	X*
Modified Rankin Scale score	X		X	X	X	X		
NIHSS score	X	As required						
QOL Assessment (EQ-5D)					X			
Additional scales as appropriate		X			X	X	Optional	Optional
Technical events		X						
Adverse events		X	X	X	X	X	X	X
Retreatments /Additional Procedures				X	X	X	X	X
Rebleed (if ruptured)/New bleed			X	X	X	X	X	X
Comments	X	X	X	X	X	X	X	X

* Per local Standard of Care

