1.2 Analysis Populations

The subject populations represented in the final analyses will be determined after CEA adjudication of all AEs and Protocol Deviations. The analysis populations include:

- The intent to treat (ITT) population includes every study subject in whom there is an attempt to place the WEB device. The primary safety and effectiveness analyses will be performed on this population.
- The completed cases (CC) population includes the group of subjects who complete the 12 month visit. Supportive analyses of the primary safety and effectiveness endpoints will be completed with this population.
- The per-protocol (PP) population includes all CC cases who additionally meet all study eligibility criteria, have available study data for the study endpoint and do not have a major protocol violation that affects primary safety or effectiveness. Selected sensitivity analyses will be done with the PP population.

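### The effectiveness endpoint counts only recurrent subarachnoid hemorrhage as a failure, so a first bleed from an unruptured index aneurysm after treatment can be scored a success

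*Protocol*

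**What the plan says.** The Primary Endpoints entry of the protocol synopsis defines effectiveness as "complete aneurysm occlusion without retreatment, recurrent subarachnoid hemorrhage, without significant parent artery stenosis" above 50%, assessed one year after treatment. The rule is then closed: "A subject will be considered an effectiveness success upon meeting all of the above criteria". Recurrent subarachnoid hemorrhage (SAH) is the only bleeding criterion. SAP 1.6 gives the hypotheses but does not restate the composite.

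Four other places bear on the point.

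- **Eligibility.** Inclusion criterion 2 reads: "Patient must have a single ruptured or unruptured IA requiring treatment".
- **Terms for bleeding.** Table 1 of the protocol has a row "Rebleed (if ruptured)/New bleed". SAP 1.12 likewise lists rebleed rates for ruptured aneurysms and new-bleed rates for unruptured ones, with a separate Kaplan-Meier analysis for each.
- **Primary safety.** A major stroke is an "ischemic or hemorrhagic stroke resulting in an increase of 4 points or more" on the NIHSS. Non-accidental death or major stroke counts to day 30. From day 31 to one year, only major ipsilateral stroke or neurologic death counts.
- **Population.** SAP 1.2 defines the ITT population by an attempt to place the device and adds: "The primary safety and effectiveness analyses will be performed on this population". SAP 1.6 instead states both hypotheses in the treated population.

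**The concern.** An aneurysm that has never bled has no hemorrhage to recur. Because the plan has a separate term for a first bleed and leaves it out of the composite, the literal rule does not fail a subject whose unruptured index aneurysm bleeds after treatment.

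The device is meant to protect the aneurysm. An endpoint that can credit it with success after that aneurysm has bled does not measure quite what it should. A mild bleed of this kind would count against neither of the two endpoints that decide study success. In a single-arm study, the classification should be fixed before outcomes are seen, not settled case by case.

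**Working it through.** **Step 1: follow one subject through the rules.** Take a subject with an unruptured index aneurysm who has a first SAH from it after the procedure, survives, and attends the one-year visit.

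| Rule | Applied to this subject |
|---|---|
| Complete occlusion at one year | Can be met |
| No retreatment | Can be met |
| No recurrent SAH | Met on the literal wording, as there was no earlier SAH |
| No parent artery stenosis above 50% | Can be met |
| Primary safety | Not a failure if the NIHSS rise is below 4 |
| SAP 1.5, missing data | Does not apply, as no outcome is missing |
| SAP 1.12, new-bleed reporting | Bleed is shown, but has no part in the success rule of SAP 1.7 |

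No other rule makes this subject an effectiveness failure. If the bleed did cause a major stroke, that would be a safety failure but still not, by itself, an effectiveness failure.

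**Step 2: reproduce the plan's sample size.** Inputs from SAP 1.6 and 1.10: null rate 0.203, expected rate 0.323, one-sided alpha 0.05, power 80%. For an exact binomial test, the pass mark r is the smallest count with P(X ≥ r | N, 0.203) ≤ 0.05, and power is P(X ≥ r | N, 0.323).

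- N = 84: r = 24, size 0.044, power 0.8005. This matches the plan.
- N = 95: r = 27, size 0.037, power 0.820.
- 95/0.85 = 111.8, so 112 recruited, as stated. At N = 112: r = 31, size 0.038, power 0.875.

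**Step 3: weight of one subject.** 1/112 = 0.9 percentage points; 1/95 = 1.05 points.

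**Step 4: illustration under assumed rates only.** Let d be the share of all subjects who have a first bleed and still meet every other success criterion. The documents give no value for d. Suppose that the true success rate is 0.203 and that the goal did not credit such subjects. The chance of a false pass is then P(X ≥ r | N, 0.203 + d):

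| d (points) | N = 95 | N = 112 |
|---|---|---|
| 0 | 0.037 | 0.038 |
| 0.5 | 0.048 | 0.050 |
| 1 | 0.062 | 0.066 |
| 2 | 0.097 | 0.107 |

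**Step 5: what d implies.** d is not a bleed rate. It equals the first-bleed rate among all subjects multiplied by the chance that a bled subject meets the other criteria. If that chance were 0.323 (assumed), d = 0.5, 1 and 2 points would need first-bleed rates of 0.005/0.323 = 1.5%, 0.01/0.323 = 3.1% and 0.02/0.323 = 6.2% of all subjects, including ruptured subjects, who cannot have a new bleed. If the chance were 0.203, the rates would be 2.5%, 4.9% and 9.9%.

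**Step 6: power cost of the stricter wording.** If the expected 0.323 includes such subjects as successes, power is P(X ≥ r | N, 0.323 − d):

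| d (points) | N = 95 | N = 112 |
|---|---|---|
| 0 | 0.820 | 0.875 |
| 0.5 | 0.792 | 0.851 |
| 1 | 0.761 | 0.823 |
| 2 | 0.691 | 0.758 |

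**The case against.** The strongest reply is that the gap is narrow and already visible. A miscounted subject must have an unruptured aneurysm, bleed from it, and still meet every other success criterion. To escape both primary endpoints, the bleed must also be survivable with an NIHSS rise below 4. Bleeds are recorded from discharge onward, new-bleed rates and curves are reported, and severe bleeds enter primary safety. All of this stands, and it limits the size of the problem. It does not change how the success rule classifies the subject.

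The authors may also have meant any SAH after treatment. The protocol supplied is a synopsis, so a fuller definition may exist elsewhere. If it does, this text need only be aligned with it. In what is supplied, the separate terms for rebleed and new bleed point the other way.

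A reader might go further in three directions that the documents do not support.

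- **That the type I error is inflated.** This needs a rate that the documents do not give and a goal that counted bleeds differently. If the source counted them as this trial does, there is no inflation.
- **That a different rupture mix makes the goal unsuitable.** SAP 1.8 says the goal was already adjusted for the anticipated mix of rupture status, so a difference in mix is not evidence of bias.
- **That older bleeds or undefined retreatment widen the gap.** The 60-day limit in "evidence of subarachnoid hemorrhage attributed to the index aneurysm within the last 60 days" defines a ruptured patient for eligibility. The endpoint is not tied to it, and a second bleed after an older one is recurrent in plain language. A missing definition of retreatment in an excerpted document is not evidence of a flaw.

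**Conclusion.** The concern holds as a defect in the endpoint's wording. Applied as written, the rule can score a first post-treatment bleed from an unruptured index aneurysm as an effectiveness success, and a mild, survivable one counts against neither primary endpoint.

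The effect is probably confined to very few subjects. In the illustration at N = 112, the false-pass probability reaches about the nominal 0.05 at half a point and exceeds it only beyond that. Every figure above zero rests on an assumed d and on an assumption about data that the documents do not describe. They are illustrations, not estimates, and no bias in the comparison with 0.203 has been shown.

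The case for the change is therefore one of validity. It should be made because it is cheap and removes a classification that would be hard to defend afterwards.

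**What to change.** 1. In the effectiveness endpoint, replace the recurrent-SAH criterion with: any subarachnoid hemorrhage from the index aneurysm during or after the index procedure (rebleed or new bleed). Naming the index aneurysm settles the source of the bleed, which the protocol already separates in exclusion criterion 9 ("Patient has had an SAH from a nonindex IA or any other intracranial hemorrhage within 90 days"). Naming the procedure settles intraprocedural bleeds.
2. At the same time, check whether the data behind the 0.203 goal counted bleeds in this way. If they did not, report the primary result under both definitions, because a stricter rule against an unchanged goal would work against the device.
3. State the SAP 1.6 hypotheses in the ITT population that SAP 1.2 makes primary.

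**Cost.** One phrase, one population label and one check of the source data. No new data collection is needed: Table 1 records bleeds from discharge onward, and adverse and technical events at the procedure. The observed success rate may be slightly lower, by 0.9 points per subject at N = 112. Power falls only if the expected 0.323 includes such subjects. At N = 112 it stays above 80% for a loss of 1 point and falls below it for a loss of 2 points. At N = 95 it falls below 80% already at half a point (0.792).

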1.1 General Approach

The study will use a standard, frequentist approach to statistical analysis. Descriptive statistics (mean, standard deviation, frequency charts, etc.) for baseline participant characteristics, patient disposition and other relevant study parameters will be reported.

1.2 Analysis Populations

The subject populations represented in the final analyses will be determined after CEA adjudication of all AEs and Protocol Deviations. The analysis populations include:

- The intent to treat (ITT) population includes every study subject in whom there is an attempt to place the WEB device. The primary safety and effectiveness analyses will be performed on this population.
- The completed cases (CC) population includes the group of subjects who complete the 12 month visit. Supportive analyses of the primary safety and effectiveness endpoints will be completed with this population.
- The per-protocol (PP) population includes all CC cases who additionally meet all study eligibility criteria, have available study data for the study endpoint and do not have a major protocol violation that affects primary safety or effectiveness. Selected sensitivity analyses will be done with the PP population.

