1.5 Missing Data

Subjects whose data are not missing at random, such as those who exit the study due to a device-related primary safety event will be imputed as a safety and effectiveness failure. These subjects are not missing at random. Subjects who are absent at twelve months and missing at random will have their success or failure imputed for the primary effectiveness endpoint by multiple imputations with random selection from subjects with outcomes with similar aneurysm locations, rupture status and if indicated, aneurysm size or geographic location, followed by sensitivity analyses.

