1.7 Study Success

The study will be considered a success if both the primary effectiveness endpoint and the primary safety endpoint are met.

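### The completed-cases population requires a 12-month visit, so the supportive safety analysis drops every fatal safety failure that occurs before that visit

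*SAP*

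**What the plan says.** SAP section 1.2 defines three populations. ITT, meaning every attempted placement, carries the primary analyses. For the second it says: "The completed cases (CC) population includes the group of subjects who complete the 12 month visit", and then: "Supportive analyses of the primary safety and effectiveness endpoints will be completed with this population". The third is nested in the second: "The per-protocol (PP) population includes all CC cases who additionally meet all study eligibility criteria". Of this one the SAP says only: "Selected sensitivity analyses will be done with the PP population".

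The Protocol (section 1, Primary Endpoints) defines a safety failure in two periods. Up to day 30 it is "death of any nonaccidental cause or any major stroke". After that it is "major ipsilateral stroke or death due to neurologic cause from day 31 to the 1 year after treatment".

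SAP section 1.5 treats some missing outcomes as not missing at random. Its example is that "those who exit the study due to a device-related primary safety event will be imputed as a safety and effectiveness failure". It does not mention membership of CC. On the decision rule, section 1.7 says: "The study will be considered a success if both the primary effectiveness endpoint and the primary safety endpoint are met".

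**The concern.** The condition for entering CC depends on the outcome being measured. Nonaccidental death to day 30 and neurologic death to one year are endpoint events, and either one makes the 12-month visit impossible. The number of pre-visit fatal failures counted in CC is therefore zero by construction. Survivors of a major stroke stay in if they attend and drop out if they do not. These outcomes are not missing: section 1.2 fixes the populations after adjudication, so the events are known when they are discarded. PP is a subset of CC, so any safety analysis run on it has the same gap.

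A supportive analysis is meant to show whether the ITT result survives a different handling of incomplete follow-up. One that cannot count fatal events does not test that for safety. Agreement between CC and ITT would give little reassurance.

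**Working it through.** **Inputs from the documents (SAP section 1.10).** Expected safety event rate 0.147, performance goal 0.28, loss to follow-up about 15%, recruited size 112.

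**Check of the plan's own figures.** For 0.147 against 0.28, an exact one-sided binomial test at 0.05 (the level is stated for effectiveness and assumed here for safety) first reaches 80% power at n = 62: success if at most 11 events, attained alpha 0.044, power 0.807. This matches the SAP's 62. Likewise 95/0.85 = 111.8, giving 112. The planning figures are not in dispute.

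**Notation.** p is the true event rate. f is the share of events that prevent the 12-month visit, through death or through a survivor missing it. The documents do not give f, so 10%, 25% and 50% are assumptions.

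**(a) Other loss unrelated to events.** The retained fraction cancels, so CC rate = p(1 − f)/(1 − pf). Example: 0.147 × 0.75/(1 − 0.03675) = 0.11025/0.96325 = 0.1145 (0.11446).

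**(b) The SAP's 15% loss taken as all event-free and additional to event-caused absence.** CC rate = p(1 − f)/(0.85 − pf). Example: 0.11025/(0.85 − 0.03675) = 0.11025/0.81325 = 0.1356.

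| True rate p | f | CC rate, (a) | CC rate, (b) |
|---|---|---|---|
| 14.7% | 10% | 13.4% | 15.8% |
| 14.7% | 25% | 11.4% | 13.6% |
| 14.7% | 50% | 7.9% | 9.5% |
| 28% | 10% | 25.9% | 30.7% |
| 28% | 25% | 22.6% | 26.9% |
| 28% | 50% | 16.3% | 19.7% |

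In (a) CC is below the true rate for any f above zero. In (b), setting the CC rate equal to p gives f = 0.15/(1 − p): 17.6% at p = 0.147 and 20.8% at p = 0.28. CC is too low only above those values.

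**Observed events discarded.** At N = 112 and p = 0.147, 112 × 0.147 = 16.5 events are expected. Multiplying by f gives 1.6, 4.1 or 8.2 discarded, in (a) and (b) alike.

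**Count example, no other loss.** With 16 failures in 112 (14.3%), 4 of them fatal before the visit, CC gives 12/108 = 11.1%.

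**The case against.** The strongest reply is that nothing is decided on CC. Primary safety is tested on ITT, which keeps these events, and the SAP attaches no test to CC. Section 1.12 separately reports mortality, overall survival and survival free from major stroke. That stands: deaths are not hidden and the trial's conclusion does not depend on this. But section 1.12 does not list the primary safety composite, and CC is the population the SAP names for supporting that composite.

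Section 1.5 might be read as a rescue. Its device-related exit is only an example, so the rule may cover other fatal events. Even so, it assigns an outcome and does not place a deceased subject among those who attended at 12 months.

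The direction of bias is not established. This stands too: in (b) at f = 10%, CC overstates risk. Scenario (b) also adds event-caused absence to the 15%. If the 15% is total non-completion, the CC rate is p(1 − f)/0.85: 15.6%, 13.0% and 8.6% at p = 0.147, and 29.6%, 24.7% and 16.5% at p = 0.28, with break-even at f = 15% for either rate. The figures move, but the defect does not.

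Finally, under (b) the amended set proposed below is further from the truth than the present CC in four of the six cases. Its error is +2.6 points at p = 0.147 and +4.9 at p = 0.28. The present errors at f = 10% and 25% are +1.1 and −1.1, and +2.7 and −1.1; only at f = 50% is the amended set closer. This is correct, but the present rule comes closer there only because discarding known events happens to offset losing event-free subjects.

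On PP, the SAP does not say that any of its sensitivity analyses concern safety, so that part is conditional.

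**Conclusion.** The concern holds. As written, the supportive primary-safety analysis excludes every endpoint death before the 12-month visit, and no other provision restores them. This conclusion follows from the definitions and needs no assumption.

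The size and sign of the effect do rest on assumptions about f and about who else is lost. If other loss is unrelated to events, the bias favours the device, by 1.3 to 6.8 points at a true 14.7% (14.7 − 13.4; 14.7 − 7.9) over the f range shown. If a 15% loss is all event-free, the sign depends on f. The consequence is limited to a supportive analysis, but the rule should be corrected because that analysis cannot do its job for safety.

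**What to change.** In SAP section 1.2, for the primary safety endpoint only, define CC as subjects who attend at 12 months or have an adjudicated primary safety event before that visit. Build any PP safety analysis on the same set, counting the event as available endpoint data. Leave the effectiveness definition of CC unchanged. Add that the safety CC rate keeps all observed events and drops event-free losses, so it is biased upward and is to be read beside the ITT rate.

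The cost is one or two sentences and no new data. With event-free loss L, the amended rate is p/(1 − L). At L = 15%, a true 14.7% appears as 0.147/0.85 = 17.3% and a true 28% as 0.28/0.85 = 32.9%. At L = 5% (an assumption) the figures are 15.5% and 29.5%. With no event-free loss the rate is p itself. The advantage over the present rule is a bias of known, conservative direction, with no observed failure discarded.
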